1. OBJECTIVES

1.1 Study Design

This is a single-arm, two-stage Phase 2 study assessing the efficacy of AZD1775, a Wee1 tyrosine kinase inhibitor, given in combination with cisplatin chemotherapy. The population to be studied will consist of approximately 35 patients with metastatic triple-negative breast cancer who have received 0 to 1 line of chemotherapy in the metastatic setting. All patients must have measurable disease at baseline and have archival tissue available. Treatment will consist of one cycle of cisplatin monotherapy (cisplatin 75 mg/m2 IV x1) followed by combination therapy of AZD1775 plus cisplatin starting 21 days later. AZD1775 will be administered as twice daily oral dosing (AZD1775 200 mg po bid) x 5 doses over 2.5 days, in combination with cisplatin 75 mg/m2 IV every 21 days. At least 10 patients will undergo a research biopsy within 5-48 hours after cisplatin monotherapy and then again within 5-8 hours after the last dose of AZD1775 in cycle 2 of cisplatin +AZD1775. Patients will undergo restaging scans every 6 weeks, those with complete responses, partial responses, and stable disease, will continue to receive study treatment. Patients with progressive disease will be taken off study.

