- 3.1.15 Appropriate contraception should be used from the time of screening, throughout the duration of study participation, and for four months after the last dose of AZD1775. Acceptable methods of contraception include abstinence, tubal ligation, intra-uterine devices, and vasectomised partner. All methods of contraception (with the exception of total abstinence) should be used in combination with the use of a condom by the male sexual partner for intercourse. Should a woman become pregnant or suspect she is pregnant while she or her partner is participating in this study, the participants treating physician should be informed immediately. Additionally, male patients should refrain from donating sperm from the start of dosing until 6 months after discontinuing AZD1775. If male patients wish to father children they should be advised to arrange for freezing of sperm samples prior to the start of study treatment.
- 3.1.16 Participant must be able to swallow pills.
- 3.1.17 Participant may not have a percutaneous endoscopic gastrostomy (PEG) tube or be receiving total parenteral nutrition (TPN).
- 3.1.18 Ability to understand and the willingness to sign a written informed consent document.

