5. TREATMENT PLAN

5.1 Treatment Regimen

Treatment will consist of one cycle (21 days) of cisplatin monotherapy (cisplatin 75 mg/m2 IV) followed by combination therapy of AZD1775 plus cisplatin starting 21 days later. AZD1775 will be administered as twice daily oral dosing (AZD1775 200mg po bid) x 5 doses for 2.5 days, in combination with cisplatin 75 mg/m2 IV every 21 days. Cycle length is 21 days long. Treatment will be administered on an outpatient basis. Reported adverse events and potential risks are described in Section 7. Appropriate dose modifications are described in Section 6. No investigational or commercial agents or therapies other than those described below may be administered with the intent to treat the participant's malignancy.

	Regimen Description				
Agent	Premedications; Precautions	Dose	Route***	Schedule	Cycle Length
AZD1775*	See Section 5.4	200 mg	PO	Twice daily x 5 doses From Cycle 2	21 days (3 weeks)
Cisplatin	See Section 5.3.2	75 mg/m2	IV 60 minutes	Days 1 From Cycle 1	

* The participant will be requested to maintain a medication diary of each dose of medication. The medication diary will be returned to clinic staff at the end of each cycle.

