5.6 Duration of Follow Up

Participants will be followed on-study until progression or death, whichever occurs first. Participants removed from protocol therapy for unacceptable adverse event(s) will be followed until resolution or stabilization of the adverse event.

The participant's treatment status will be updated in OnCore at the time treatment with cisplatin and AZD1775 is discontinued.

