5.7 Criteria for Taking a Participant Off Study

Participants will be removed from study when any of the following criteria apply:

- Disease Progression (in patients who come off treatment for reasons other than progressive disease)
- Lost to follow-up
- Withdrawal of consent for data submission
- Death

The reason for taking a participant off study, and the date the participant was removed, must be documented in the case report form (CRF) and Clinical Trial Management System (OnCore).

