6.1 Dose Delays and Modifications for AZD1775

Participants can have a maximum of 2 dose modifications (if applicable) throughout the course of the study for toxicities. Participants who require more than 2 dose modifications may remain on study and continue with cisplatin monotherapy per investigator discretion. In the event that a participant is not willing to dose reduce AZD1775, they may continue with cisplatin monotherapy per investigator discretion.

In the event of toxicity, it is recommended that the investigator first modify the dose of AZD1775; however the investigator may choose to first modify the chemotherapy dose instead, in consultation with the Principal Investigator. If a second dose reduction is necessary during combination therapy, the dose of chemotherapy or AZD1775 may be modified. This decision should be made jointly by the treating physician and the Principal Investigator. Participants who experience toxicity that the investigator finds attributable to AZD1775 will have their AZD1775 dose reduced by 1 dose level as shown in Table 6-1. A participant's dose may be re-escalated at the discretion of the principal investigator.

If Day 1 dosing is delayed, all assessments will be delayed to accordingly.

Table 6-1 DOSE MODIFICATION OF AZD1775

Dose Level	AZD1775 Dose
0	200mg, twice daily x 5 doses
-1	175mg, twice daily x 5 doses
-2	150mg, twice daily x 5 doses
-3	125mg, twice daily x 5 doses

Nausea	Management/Next Dose for AZD1775
≤ Grade 1	No change in dose
Grade 2	Hold until ≤ Grade 1. Resume at same dose level.
Grade 3	Hold* until < Grade 2. Resume at one dose level lower, if indicated.**
Grade 4	Discontinue treatment and follow for disease progression
4	

^{*}Participants requiring a delay of >3 weeks should discontinue AZD1775.

All patients must receive a 5-HT3 antagonist prior to each dose of AZD1775. Additional doses of 5-HT3 antagonist may be used if needed. In addition, dexamethasone 4 mg PO will be given with each AZD1775 dose as a minimum on the first day of dosing AZD1775 of every 3-5 days dosing period, unless contraindicated or not well-tolerated. Dexamethasone may be continued on further days of dosing, potentially at a lower dose. Dexamethasone or the 5-HT3 antagonist may be given by IV.

Promethazine (Phenergan), prochlorperazine (Compazine), and benzodiazepine may still be used as additional adjunctive treatments during AZD1775 therapy.

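### Section 3.1.15 counts the contraception and sperm-donation windows from AZD1775 only, so a patient whose last or only study drug is cisplatin can be left with too short a window or none defined

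*Combined protocol and SAP*

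**What the plan says.** Section 3.1.15 asks for contraception "from the time of screening, throughout the duration of study participation, and for four months after the last dose of AZD1775". It adds that "male patients should refrain from donating sperm from the start of dosing until 6 months after discontinuing AZD1775". Both post-treatment periods are tied to AZD1775, and the supplied text sets no separate period for cisplatin.

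The two drugs do not always stop together. Section 5.1 opens with cisplatin alone: "Treatment will consist of one cycle (21 days) of cisplatin monotherapy". AZD1775 begins on Cycle 2 Day 1 (Section 10). Under Section 6.1, patients who need more than two dose modifications "may remain on study and continue with cisplatin monotherapy per investigator discretion". The same option is open to patients who decline an AZD1775 reduction. No maximum number of cisplatin-only cycles is given.

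The end of participation is described in several ways:

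- Section 1.1: "Patients with progressive disease will be taken off study".
- Section 5.6: "Participants will be followed on-study until progression or death, whichever occurs first".
- Section 5.7 lists progression as an off-study reason only for patients who stopped treatment for another reason. It also lists "Withdrawal of consent for data submission".
- A footnote to the Section 10 calendar has survival contacts every six months.

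**The concern.** A window meant to protect against conception after exposure to study treatment should start at the last exposure. Here it starts at the last dose of one of the two drugs, and that dose can come well before the last dose of the other or never be given at all.

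The protocol itself gives reason to include cisplatin. Section 2.3 describes it as DNA-damaging. Section 8.2.1 says platinum can be found in tissue up to 180 days after dosing. Section 3.2.12, on breastfeeding, accepts that the risk may extend to the other study agents. Section 3.1.15 does not carry that over.

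What is at stake is participant safety: possible fetal exposure, or sperm donation, soon after cisplatin. The response rate, the two-stage rule and its error rates do not depend on this.

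**Working it through.** The plan gives no figure to reproduce, so the check is calendar arithmetic.

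**Inputs**
- Contraception window D: four months from the last AZD1775 dose (3.1.15), taken as 122 days, range 120 to 123.
- Sperm-donation ban: six months from stopping AZD1775 (3.1.15), taken as 183 days. The range 180 to 184 gives the same answer.
- AZD1775: five doses over 2.5 days (5.1), so the last dose is on Day 3 of its cycle.
- Cisplatin: Day 1 of each 21-day cycle (5.1), assumed without delay.
- m: the number of cisplatin-only cycles after the last AZD1775 dose. This is an assumption, shown as a range because the protocol sets no limit.

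**Contraception.** The m-th cisplatin-only dose falls 21m − 2 days after the last AZD1775 dose. The AZD1775-based window left after that cisplatin dose is max(0, D − (21m − 2)), which for D = 122 is max(0, 124 − 21m).

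| m | Days from last AZD1775 dose to last cisplatin dose | Days left, D = 122 | Days left, D = 120 to 123 |
|---|---|---|---|
| 1 | 19 | 103 | 101–104 |
| 2 | 40 | 82 | 80–83 |
| 3 | 61 | 61 | 59–62 |
| 4 | 82 | 40 | 38–41 |
| 5 | 103 | 19 | 17–20 |
| 6 | 124 | 0 | 0 |

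At m = 6 the window has closed before the last cisplatin dose (122 − 124 = −2), so any remaining cover comes only from still being on study. If both drugs stop in the same cycle, the window runs 122 + 2 = 124 days past cisplatin and there is no shortfall.

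**Sperm donation.** This sentence has no participation clause. The smallest m with 21m − 2 > 183 is m = 9 (21 × 9 − 2 = 187), so the ban has ended before the ninth cisplatin-only dose. If AZD1775 is instead treated as discontinued on the first Day 1 at which it is omitted, the condition is 21(m − 1) > 183. That gives m = 10 (21 × 9 = 189).

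**Cycle 1 only.** There is no AZD1775 dose, so the four-month clock never starts. The sperm-donation ban starts with dosing but has no defined end.

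**Can such a patient leave the study?** Yes. Section 11.1.1 provides for progression before the end of cycle 1. Section 6.2 withdraws patients for a haematological delay of more than three weeks. It also takes patients off study for grade 4 non-haematological toxicity attributed to cisplatin, unless an exception is granted. Section 5.7 ends participation on withdrawal of consent for data submission.

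**The case against.** The best reply is that the participation clause does most of the work. Contraception stays in force through every cisplatin-only cycle. A patient who stops treatment without progression is normally followed until progression, with scans every six to nine weeks. The survival contacts might extend participation further. A patient who leaves at a scheduled Day 21 scan has already had about 20 days of cover since the last cisplatin dose (13 to 27 with the seven-day tolerance). This is right, and it means the table shows the AZD1775-based window rather than total cover after cisplatin. It does not close the gap, because the protocol does not settle when participation ends and Section 6.2 provides routes off study for toxicity.

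The affected groups are also narrow. The first scheduled scan is at Cycle 2 Day 21, so leaving after cycle 1 needs early progression, toxicity or withdrawal. A lapse of the sperm-donation ban during treatment needs a male patient with at least 1 + 1 + 9 = 11 cisplatin doses, the last 10 × 21 = 210 days after the first. Section 6.2 describes cumulative renal toxicity and late neuropathy, which make that uncommon. For a man given cycle 1 only, the ban is open-ended and unclear rather than short. These points limit how many patients are affected, but the wording fault remains.

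Finally, tissue persistence does not set a required duration. The 180-day figure exceeds four months even for patients on the combination throughout, and the documents give no cisplatin standard. The consent pages were removed before review and may advise on cisplatin. Both points stand. They are why the fix changes the starting point of the windows and leaves the durations to the sponsor.

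**Conclusion.** The concern holds. Followed exactly, Section 3.1.15 gives less protection to a patient whose last or only study drug is cisplatin than to one on the combination to the end. With one to five cisplatin-only cycles the remaining window falls from 103 to 19 days, and at six it is gone. After cycle 1 alone there is no defined contraception window once participation ends, and no defined end to the sperm-donation ban.

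These figures assume undelayed 21-day cycles and a last AZD1775 dose on Day 3. The contraception gap also requires participation to end soon after the last cisplatin dose, for example at progression or on withdrawal. How many patients would be affected cannot be told from the documents and is probably small. This is a participant-safety wording point that should be corrected. It has no bearing on the statistical conclusions.

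**What to change.** In Section 3.1.15, count both the contraception window and the sperm-donation window from the last dose of AZD1775 or cisplatin, whichever is later. Every patient, including one who received cycle 1 only, would then have a defined window of about 122 days for contraception and 183 days for sperm donation after the last exposure. The sponsor should confirm that four and six months are adequate for cisplatin, and the consent text should match.

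The cost is a few words in one criterion, a matching consent edit and slightly longer contraception for a few patients. No visit or test is added.

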3.2 Exclusion Criteria

- 3.2.1 Participants who are receiving any other investigational agents within 21 days of the first dose of study drug.
- 3.2.2 Major surgical procedures <28 days from beginning study treatment.
- 3.2.3 Participants who have received a prior inhibitor of Weel kinase activity
- 3.2.4 Participants who have received prior platinum chemotherapy
- 3.2.5 Known brain metastases that are untreated, symptomatic, or require therapy to control symptoms. Patients with a history of treated central nervous system (CNS) metastases are eligible. Treated brain metastases are defined as those having no evidence of progression for ≥ 1 month after treatment, or hemorrhage for >/= 2 weeks after treatment and no ongoing requirement for corticosteroids, as ascertained by clinical examination and brain imaging (magnetic resonance imaging or CT scan) during the screening period. Any corticosteroid use for brain metastases must have been discontinued without the subsequent appearance of symptoms for ≥2 weeks before the first study drug. Treatment for brain metastases may include whole brain radiotherapy, radiosurgery, or a combination as deemed appropriate by the treating physician. Patients with CNS metastases treated by neurosurgical resection or brain biopsy performed within 1 month before day 1 of study treatment will be excluded.
- 3.2.6 Patients with grade >1 neuropathy or grade >1 toxicity (except alopecia or anorexia) from prior therapy
- 3.2.7 History of allergic reactions attributed to compounds of similar chemical or biologic composition to AZD1775 or Cisplatin.
- 3.2.8 Participants receiving any medications, substances, or foods (ie, grapefruit juice) listed below are ineligible (Please refer to Section 5.4 for list of restricted comedications):

- prescription or non-prescription drugs or other products known to be sensitive CYP3A4 substrates or CYP3A4 substrates with a narrow therapeutic index, or to be moderate to strong inhibitors/inducers of CYP3A4 which cannot be discontinued prior to study start and withheld throughout the study until 2 weeks after the last dose of study drug. sensitive substrates of CYP2C8, CYP2C9, CYP2C19, or substrates of these enzymes with narrow therapeutic range
- inhibitors or substrates of P-gp

Because the lists of these agents are constantly changing, it is important to regularly consult a frequently-updated list such as

http://medicine.iupui.edu/clinpharm/ddis/table.aspx; medical reference texts such as the Physicians' Desk Reference may also provide this information. As part of the enrollment/informed consent procedures, the patient will be counseled on the risk of interactions with other agents, and what to do if new medications need to be prescribed or if the patient is considering a new over-the-counter medicine or herbal product.

- 3.2.9 Participants who have an uncontrolled intercurrent illness, including, but not limited to, ongoing or active infection, uncontrolled hypertension, unstable angina pectoris, uncontrolled cardiac arrhythmia, congestive heart failure-New York Heart Association Class III or IV (Appendix B), active ischemic heart disease, myocardial infarction within the previous six months, uncontrolled diabetes mellitus, gastric or duodenal ulceration diagnosed within the previous 6 months, chronic liver or renal disease, or severe malnutrition. In addition, patients are ineligible if they have a psychiatric illness or a social situation that could limit their ability to comply with the study requirements.
- 3.2.10 Participants who have refractory nausea and vomiting, chronic gastrointestinal diseases, or previous significant bowel resection that would preclude adequate absorption of AZD1775.
- 3.2.11 Pregnant women are excluded from this study because AZD1775 is a Weel inhibitor agent with the potential for teratogenic or abortifacient effects.
- 3.2.12 Lactating or breastfeeding women are excluded because there is an unknown but potential risk for adverse events in nursing infants secondary to treatment of the mother with AZD1775, breastfeeding should be discontinued prior to being treated with AZD1775. These potential risks may also apply to other agents used in this study.
- 3.2.13 Known HIV-positive participants are ineligible because these participants are at increased risk of lethal infections when treated with marrow-suppressive therapy.
 - 3.2.14 Participant with mean resting corrected QT interval (specifically QTc calculated using the Fridericia formula [QTcF]) > 450 msec for males and > 470 msec for females, from 3 electrocardiograms (ECGs) performed within 2-5 minutes apart at study entry, or congenital long QT syndrome.

3.3 Inclusion of Women and Minorities

Both men and women of all races and ethnic groups are eligible for this trial.

4. REGISTRATION PROCEDURES

4.1 General Guidelines for DF/HCC Institutions

Institutions will register eligible participants in the Clinical Trials Management System (CTMS) OnCore. Registrations must occur prior to the initiation of protocol therapy. Any participant not registered to the protocol before protocol therapy begins will be considered ineligible and registration will be denied.

An investigator will confirm eligibility criteria and a member of the study team will complete the protocol-specific eligibility checklist.

Following registration, participants may begin protocol therapy. Issues that would cause treatment delays should be discussed with the Overall Principal Investigator (PI). If a participant does not receive protocol therapy following registration, the participant's registration on the study must be canceled. Registration cancellations must be made in OnCore as soon as possible.

4.2 Registration Process for DF/HCC Institutions

DF/HCC Standard Operating Procedure for Human Subject Research Titled *Subject Protocol Registration* (SOP #: REGIST-101) must be followed.

5. TREATMENT PLAN

5.1 Treatment Regimen

Treatment will consist of one cycle (21 days) of cisplatin monotherapy (cisplatin 75 mg/m2 IV) followed by combination therapy of AZD1775 plus cisplatin starting 21 days later. AZD1775 will be administered as twice daily oral dosing (AZD1775 200mg po bid) x 5 doses for 2.5 days, in combination with cisplatin 75 mg/m2 IV every 21 days. Cycle length is 21 days long. Treatment will be administered on an outpatient basis. Reported adverse events and potential risks are described in Section 7. Appropriate dose modifications are described in Section 6. No investigational or commercial agents or therapies other than those described below may be administered with the intent to treat the participant's malignancy.

	Regimen Description				
Agent	Premedications; Precautions	Dose	Route***	Schedule	Cycle Length
AZD1775*	See Section 5.4	200 mg	PO	Twice daily x 5 doses From Cycle 2	21 days (3 weeks)
Cisplatin	See Section 5.3.2	75 mg/m2	IV 60 minutes	Days 1 From Cycle 1	

* The participant will be requested to maintain a medication diary of each dose of medication. The medication diary will be returned to clinic staff at the end of each cycle.

5.2 Pre-Treatment Criteria

5.2.1 Cycle 1, Day 1

- ANC must be $\geq 1500/\text{mm}^3$
- Hemoglobin must be $\geq 9 \text{mg/dl}$
- Platelets must be $\geq 100,000/\text{mm}^3$
- Serum creatinine < 1.5mg/dl OR measured creatinine clearance (CrCl) ≥45 mL/min as calculated by the Cockcroft-Gault method OR 24-hour measured urine CrCl ≥45mL/min
- SGOT/SGPT must be $\leq 2.5 \text{ X ULN}$ ($\leq 5 \text{ X ULN}$ if known liver metastases)
- Total Bilirubin ≤1.5 mg/dL

5.2.2 Subsequent Cycles

- ANC must be $\geq 1000/\text{mm}^3$
- Hemoglobin must be ≥9mg/dl
- Platelets must be $\geq 75,000/\text{mm}^3$
- Serum creatinine ≤1.5 x ULN, or measured creatinine clearance (CrCl) ≥45 mL/min as calculated by the Cockcroft-Gault method or 24-hour measured urine CrCl ≥45mL/min
- Transaminitis must return to \leq grade 2
- Diarrhea must be resolved \leq grade 1.
- Nausea and Vomiting must return to ≤ grade 1
- Neurosensory must be \leq grade 2
- Other Treatment Related non-Hematologic Toxicity must return to ≤ grade 1

